4.1.3. Baseline Value

Baseline is the last nonmissing measurement obtained before the first administration of tafasitamab or parsaclisib, unless otherwise defined.

When scheduled assessments and unscheduled assessments occur on the same day and the time of the assessment or time of first dose is not available, use the following convention to determine baseline:

- If both a scheduled and an unscheduled visit are available on the day of the first dose and the time is missing, use the scheduled assessment as baseline.
- If all scheduled assessments are missing on the day of the first dose and an unscheduled assessment is available, use the unscheduled assessment as baseline.

4.1.4. Handling of Missing and Incomplete Dates

In general, values for missing dates will not be handled unless methods for handling missing dates are specified in this section or relevant sections. The original reported dates collected on the eCRF should be used in all relevant listings. The following rules will be used for handling partial dates for analyses requiring dates.

When calculating the time since diagnosis of disease, a partial disease diagnosis date will be handled as follows in the calculation:

- If only the day is missing, then the first day of the month will be used.
- If both the month and day are missing, then 01 JAN of the year will be used.
- If the diagnosis date is completely missing, then the time since diagnosis will not be calculated.

When the date of the last dose is used in deriving variables such as duration of treatment or TEAE flag, a missing or partial date of the last dose will be handled as follows:

- If only the day is missing, then the earlier date of the last day of the month or the date that the participant discontinued treatment will be used.
- If both the month and day are missing, then the earlier date of 31 DEC of the year or the date that the participant discontinued treatment will be used.
- Otherwise, the date that the participant discontinued treatment will be used as the date of the last dose.

For relevant efficacy endpoints, a partial date of the death date will be handled as follows in the calculation:

- If mmYYYY for the last known alive date = mmYYYY for the death date, then the death date will be set to the day after the last known alive date.
- If mmYYYY for the last known alive date < mmYYYY for the death date, then the death date will be set to the first day of the death month.
- Otherwise, the partial death date will not be imputed.

4.1.5. Cycle Length and Duration

Cycle 1 Day 1 is the day that the first dose of tafasitamab or parsaclisib is administered. The scheduled cycle length is 28 days. The actual Day 1 of subsequent cycles will correspond with the first day of administration of tafasitamab or parsaclisib in that cycle; thus, treatment cycles may become out of sync with the originally planned schedule, and the cycle length may be different from 28 days. The date of the Day 1 of subsequent cycles recorded on the eCRF will be used as the Day 1 of the subsequent cycles.

4.2. Variable Definitions

The following variables will only be calculated if not reported on the eCRF.

4.2.1. Body Mass Index

Body mass index will be calculated as follows:

$$\text{Body mass index (kg/m}^2\text{)} = [\text{weight (kg)}] / [\text{height (m)}]^2.$$

4.2.2. Prior and Concomitant Medication

Prior medication is defined as any nonstudy medication started before the first dose of tafasitamab or parsaclisib.

Concomitant medication is defined as any nonstudy medication that is started accordingly:

- Before the date of first administration of tafasitamab or parsaclisib and is ongoing throughout the study or ends on/after the date of first study drug administration.
- On/after the date of first administration of tafasitamab or parsaclisib and is ongoing or ends during the course of study.

A prior medication could also be classified as "both prior and concomitant medication" if the end date is on or after first dose of tafasitamab or parsaclisib. In the listing, it will be indicated whether a medication is only prior, only concomitant, or both prior and concomitant.

For the purposes of analysis, all medications will be considered concomitant medications unless the medications can unequivocally be defined as not concomitant.

5. STATISTICAL METHODOLOGY

5.1. General Methodology

Unless otherwise noted, SAS® software (SAS Institute Inc, Cary, NC; v9 or later) will be used for the generation of all tables, graphs, and statistical analyses. Descriptive summaries for continuous variables will include but not be limited to the number of observations, mean, standard deviation, median, minimum, and maximum. Descriptive summaries for categorical variables will include the number and percentage of participants in each category.

5.2. Treatment Groups

This is an open-label, single treatment group study. Participants will be summarized overall by total only for each disease-specific cohort.

5.3. Analysis Populations

5.3.1. All-Screened Population

The all-screened population will include all participants who signed the informed consent form.

5.3.2. Full Analysis Set

The FAS will include all participants who received at least 1 dose of tafasitamab or parsaclisib. The FAS will be used for the summary of demographics, baseline characteristics, participant disposition, and analyses of all safety and efficacy data.

5.3.3. Efficacy Evaluable Set

The efficacy evaluable population will include all participants enrolled in the study who have received at least 1 dose of tafasitamab or parsaclisib and completed a baseline scan and meet at least one of the following criteria:

- ≥ 1 postbaseline scan.
- Participation in the study for a minimum of 42 days.
- Discontinued from treatment or died prior to the first scheduled postbaseline scan.

5.3.4. Dose-Limiting Toxicity Evaluable Population

The DLT evaluable population will include participants who have received at least 3 of 4 doses of tafasitamab and 21 days of treatment with parsaclisib 20 mg QD during the first cycle (28 days) or have experienced a DLT. Participants who are considered not evaluable will be replaced.

5.3.5. Pharmacokinetic Evaluable Population

The PK evaluable population will include all participants who received at least 1 dose of tafasitamab or parsaclisib and provided at least 1 postdose PK plasma sample.

5.3.6. Immunogenicity Analysis Set

The immunogenicity analysis set will include all participants who received at least 1 dose of tafasitamab or parsaclisib and have at least 1 evaluable antitafasitamab antibody (ADA) assessment.

6. BASELINE, EXPOSURE, AND DISPOSITION

[Appendix A](#) provides a list of data displays. Sample data displays are included in a separate document.

6.1. Demographics, Baseline Characteristics, and Disease History

6.1.1. Demographics and Baseline Characteristics

The following demographics and baseline characteristics will be summarized for the FAS: age, sex, race, ethnicity, weight, height, and body mass index.

6.1.2. Baseline Disease Characteristics

The following baseline disease characteristics will be summarized for the FAS: ECOG performance status.

6.1.3. Disease History

The date of initial diagnosis, time since diagnosis, and initial presence of B symptoms will be summarized and listed for all cohorts.

Time since diagnosis will be calculated as follows:

$$\text{Time since diagnosis (years)} = (\text{Day 1 date} - \text{date of diagnosis} + 1) / 365.25.$$

For Cohort 1 (R/R DLBCL), initial DLBCL type, initial stage, current stage, NCCN-IPI at initial diagnosis, and NCCN-IPI at current diagnosis will be summarized and listed.

For Cohort 2 (R/R MCL), initial cytogenetics, current cytogenetics, initial Ann Arbor stage, current Ann Arbor stage, initial vitamin D information, current vitamin D information, initial blastoid variant, current blastoid variant, initial MIPI risk category, current MIPI risk category, initial beta-2 globulin, current beta-2 globulin, initial Ki-67 proliferation index, current Ki-67 proliferation index, initial CD5 surface expression, current CD5 surface expression, initial CD23 surface expression, current CD23 surface expression, initial CCND1, current CCND1, initial tp3, current tp3, initial SOX11, and current SOX11 will be summarized and listed.

For Cohort 3 (R/R FL), initial grade, current grade, initial cytogenetics, current cytogenetics, initial Ann Arbor stage, and current Ann Arbor stage will be summarized and listed.

For Cohort 4 (R/R MZL), disease subtype, current grade, initial cytogenetics, current cytogenetics, initial Ann Arbor stage, and current Ann Arbor stage will be summarized and listed.

For Cohort 5 (R/R CLL/SLL), initial Rai staging, current Rai staging, initial Rai clinical feature supporting staging, current Rai clinical feature supporting staging, initial Binet staging, current Binet staging, initial involved areas supporting Binet staging, current involved areas supporting Binet staging, initial cytogenetics, current cytogenetics, initial Ann Arbor staging, current Ann Arbor staging, and initial presence of constitutional symptoms will be summarized and listed.

If there are limited participants in 1 or more disease subtypes (eg, fewer than 5 participants in a disease-specific cohort), summaries may not be tabulated.

6.1.4. Prior Therapy

The number of prior systemic cancer therapy regimens will be summarized for all participants in the FAS. The component drugs of prior systemic therapy regimens will be coded using the WHO Drug Dictionary. The number and percentage of participants who received each drug will be summarized by WHO drug class and WHO drug PT. The regimen name, component drugs, start and stop dates, best response, reason for regimen, and date of relapse/progression will be listed.

The number of participants who received prior radiation will be summarized for the FAS. The radiotherapy type, anatomic location of the administration, start and stop dates, total dose, and best response will be listed.

The number of participants who had prior surgery or surgical procedure for malignancies under study will be summarized for the FAS. The date and description of the surgery/procedure will be listed.

The number of participants who had hematopoietic stem cell transplant will be summarized for the FAS. Date of transplant, type of transplant, source of cells, line of therapy, best response, date of relapse/progression, regimen name, and drug used with the transplant will be listed.

6.1.5. Medical History

For participants in the FAS, medical history will be summarized by assigned treatment group. This summation will include the number and percentage of participants with medical history event for each body system/organ class as documented on the eCRF.

6.2. Disposition of Participant

The number and percentage of participants who were treated, who were ongoing with study treatment, who discontinued study treatment with a primary reason for discontinuation, who were still in the study, who completed the study, and who withdrew from the study with a primary reason for withdrawal will be summarized for the FAS. The number of participants enrolled by country and/or site will also be provided for the FAS.

6.3. Protocol Deviations

Protocol deviations recorded on the eCRF will be summarized and listed.

6.4. Exposure

For participants in the safety population, exposure to tafasitamab and parsaclisib will be summarized descriptively as the following:

- Tafasitamab:
 - **Duration of tafasitamab (days):** Date of last dose of tafasitamab – date of first dose of tafasitamab + 1.
 - **Number of cycles of tafasitamab:** number of cycles of tafasitamab.
 - **Number of infusions of tafasitamab:** number of infusions of tafasitamab.
 - **Tafasitamab dose modifications:** number of participants who had tafasitamab infusion interruption and infusion delay.
- Parsaclisib:
 - **Duration of treatment with parsaclisib (days):** Date of last dose of parsaclisib – date of first dose of parsaclisib + 1.
 - **Total actual dose of parsaclisib (mg):** Total actual dose taken will be calculated based on the information entered on the Dose eCRF.
 - **Average daily dose of parsaclisib (mg/day):** total actual parsaclisib dose taken (mg) / duration of treatment with parsaclisib (days).
 - **Parsaclisib dose modifications:** number of participants who had parsaclisib dose reduction or interruption.

6.5. Dose Intensity, Relative Dose Intensity, and Study Drug Compliance

For participants in the FAS population, actual dose intensity and relative dose intensity of tafasitamab and parsaclisib will be summarized descriptively. The actual or planned dose intensity will be calculated by summing the visit-wise actual or planned doses.

6.5.1. Dose Intensity and Relative Dose Intensity of Tafasitamab

For participants in the FAS, the RDI of tafasitamab will be calculated for all participants as follows:

- ADI (unit: mg/kg): the actual dose the participant was exposed to. ADI per infusion will be derived as follows:
 - If the question "was the entire infusion administered" on the "Tafasitamab Infusion" eCRF page was answered with "yes":
ADI at the visit = tafasitamab visit dose (mg) / patient weight at the visit
 - If the question "was the entire infusion administered" on the "Tafasitamab Infusion" eCRF page was answered with "no":
ADI at the visit = (tafasitamab visit dose [mg] × [estimated volume delivered/prepared volume]) / patient weight at the visit

- Skipped doses will result in an ADI of 0 for the particular visit.
- The ADI will be calculated by summing up all infusion-wise actual doses.
- PDI (mg/kg): 12 mg/kg per infusion as per Protocol.
- **Relative dose intensity (%):** The RDI expresses the amount of drug administered compared with the planned amount of drug across all infusions.
$$RDI = ADI / (PDI \times \text{the number of infusions}) \times 100$$

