### 6.6.2.1. Tafasitamab Dose Modifications for Cytokine Release Syndrome and Infusion-Related Reactions

Dose reductions of tafasitamab are not permitted. Drug interruptions or discontinuation may occur in the case of severe IRRs, allergic reactions, infections, febrile neutropenia, or severe hematologic toxicity. Delaying the tafasitamab dose is permitted for no more than 2 days (eg, if dosing was planned on Day 8, delaying that dose is allowed up to Day 10). Alternatively, an infusion of tafasitamab may be skipped completely, and the next scheduled dose will be administered (eg, if an infusion is skipped on Day 8, the next dose will be administered on Day 15). In the event tafasitamab administration is interrupted due to toxicity, other regularly scheduled assessments should still be performed.

Some mAb treatments in NHL have been associated with Grade 3 IRRs during the first infusion in participants. These IRRs have been ameliorated or eliminated by fractionating the dose into 2 infusions separated by at least 24 hours. If the full dose of tafasitamab cannot be administered in 1 day, the dose may be split into a second administration that must be given on the subsequent day. After the occurrence of a first-dose Grade 3 IRR, the next 3 infusions for this participant will be split: one-third of the dose administered on the original schedule followed by the remaining two-thirds on the next day, with each infusion administered over 2 hours. If there are no IRRs with the 3 consecutive split infusions, then the investigator can consider reverting to a single 2-hour infusion for the subsequent infusions.

Infusion-related reactions have commonly been reported for participants with CLL or NHL treated with tafasitamab. Infusion-related reaction will be defined according to the NCI CTCAE v5.0 definition of IRR and CRS. [Table 9](#) provides guidance for the management of IRRs by grade.

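### The SAP has no rule for split tafasitamab doses: read literally, its relative dose intensity falls to 57.1% after Cycle 1 in a participant who received every dose in full

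*SAP*

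**What the plan says.** SAP 6.5.1 sets the planned dose intensity (PDI) as "PDI (mg/kg): 12 mg/kg per infusion as per Protocol". For the actual dose intensity (ADI) it states: "The ADI will be calculated by summing up all infusion-wise actual doses". RDI is then ADI divided by the product of PDI and the number of infusions, times 100. The number of infusions is not defined, and split doses are not mentioned.

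Two other statements use a different unit. SAP 6.5, which introduces 6.5.1, says: "The actual or planned dose intensity will be calculated by summing the visit-wise actual or planned doses". Within 6.5.1 itself: "Skipped doses will result in an ADI of 0 for the particular visit".

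SAP 6.4 lists "Number of infusions of tafasitamab" as an exposure variable and defines it only by repeating the name.

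Protocol 6.6.2.1 provides for split doses in two situations. If a full dose cannot be given in one day, "the dose may be split into a second administration that must be given on the subsequent day". After a first-dose Grade 3 infusion-related reaction (IRR), the next three infusions are split, with "one-third of the dose administered on the original schedule followed by the remaining two-thirds on the next day, with each infusion administered over 2 hours". Returning to single infusions after three reaction-free split doses is at the investigator's discretion.

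**The concern.** The protocol attaches 12 mg/kg to a scheduled dosing day. The SAP attaches it to an infusion. The two agree until a dose is split. Then the parts (4 and 8 mg/kg under the one-third/two-thirds rule) together add 12 mg/kg to the numerator, but two infusions add 24 mg/kg to the denominator. RDI falls although nothing was missed.

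This is not a version lag. SAP 2.1 says the SAP is based on Protocol Amendment 1, and the Amendment 1 summary of changes records that provisions to split the dose were included then.

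At stake is how the exposure table reads. Protocol 10.4.1 calls for dose intensity to be summarized, and safety and tolerability are the Phase 1b primary objective. Tafasitamab dose reductions are not permitted, so a low RDI would be taken to mean skipped or incomplete infusions. Cohorts have 10 to 20 evaluable participants and SAP 5.1 reports minimums, so one such participant would be visible.

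**Working it through.** The documents state no RDI value, so there is no figure to reproduce. The check applies the SAP formula directly.

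**Inputs**
- PDI = 12 mg/kg per infusion (SAP 6.5.1).
- Schedule: Days 1, 8, 15 and 22 of Cycles 1 to 3, so 4 doses by the end of Cycle 1 and 12 by the end of Cycle 3 (Protocol 6.2.1).
- After a first-dose Grade 3 IRR the next three doses are split in two (Protocol 6.6.2.1). These are Days 8, 15 and 22 of Cycle 1.
- Assumption: every dose is delivered in full.

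**Formula, each part counted as an infusion**

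With *n* doses, of which *s* are split, there are *n* + *s* infusions, so RDI = 100 × 12*n* / [12 × (*n* + *s*)].

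Check case: 4 doses, none split, gives 48/48 = 100%.

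| Situation | Doses | Infusions | RDI |
|---|---|---|---|
| End of Cycle 1, first dose single, next 3 split | 4 | 7 | 48/84 = 57.1% |
| End of Cycle 1, first dose also split | 4 | 8 | 48/96 = 50.0% |
| End of Cycle 3, 3 split | 12 | 15 | 144/180 = 80.0% |
| End of Cycle 3, first dose also split | 12 | 16 | 144/192 = 75.0% |
| 24 doses, 3 split | 24 | 27 | 288/324 = 88.9% |
| End of Cycle 3, all but the first split | 12 | 23 | 144/276 = 52.2% |

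**Visit-wise reading**

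If both parts of a split dose belong to one scheduled dose, planned and actual are each 12 mg/kg for that dose, and RDI is 100% in every row.

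**Skipped doses**

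The choice of unit also decides whether a skipped dose counts. With 1 of 4 scheduled doses skipped and the other 3 full, RDI is 36/48 = 75% on scheduled doses but 36/36 = 100% on infusions actually given. The rule scoring a skipped dose as zero lowers RDI only with a scheduled-dose denominator.

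**The case against.** The strongest reply is that the SAP already means scheduled doses. SAP 6.5 sums by visit, 6.5.1 computes each ADI at the visit from the visit dose, and the zero for a skipped dose makes sense only if scheduled doses are counted. The protocol also uses the word infusion for a whole scheduled dose when it says the next three infusions will be split. On that reading a split dose scores 12/12.

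This stands as far as it goes: a reading that gives 100% exists. It does not settle the matter, because the operative formula in 6.5.1 is worded per infusion and the same protocol paragraph calls each part an infusion. Two programmers could follow the text and report 57.1% and 100% for the same participant.

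A reader might infer more than the documents support:

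- **That the low RDI is certain.** It depends on counting each part. How the Tafasitamab Infusion eCRF page records a split dose is not shown, and the table shells are in a separate document.
- **That 50% to 57% is typical.** It is the low end, and needs treatment to end around Cycle 1 or splitting to continue. A participant reaches 50.0% only if the first dose is split too.
- **That infusion reactions would be formally linked to under-dosing.** RDI is only summarized descriptively, and no analysis relating it to reactions is described.
- **That the SAP 6.4 infusion count is wrong.** Counting two administrations as two infusions is a legitimate convention. The gap is that 6.4 does not state which convention it uses.
- **That a frequency can be predicted.** In the tafasitamab plus idelalisib study described in Protocol 2.1.5.1, 1 of 11 participants had a Grade 3 IRR, but the text does not say it was at the first dose, which is the trigger here.

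**Conclusion.** The point holds as a conflict between SAP 6.5 and 6.5.1 and a missing split-dose rule. It is not a miscalculated figure. Followed literally, 6.5.1 gives a fully dosed participant with three split doses 57.1% at the end of Cycle 1 and 80.0% at the end of Cycle 3, or 50.0% and 75.0% if the first dose was also split. The visit-wise wording gives 100%.

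The low values assume that each part is counted as an infusion, that all doses are delivered in full and, apart from the row where splitting continues, that splitting stops after the three mandated doses. The 100% assumes that both consecutive-day parts are assigned to the same scheduled dose. How many participants would be affected cannot be estimated from the documents.

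The consequence is confined to the descriptive exposure summary. The ORR and DLT analyses do not use RDI. The correction is worth making because the rule as written can produce a wrong number and the remedy costs little.

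**What to change.** In SAP 6.5.1:
- Define PDI as the protocol dose per scheduled dosing day.
- Make the RDI denominator PDI times the number of scheduled doses, including skipped ones.
- State that the consecutive-day parts of a split dose are combined into one dose for ADI and RDI.

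In SAP 6.4:
- State whether the infusion count is of doses or of administrations.
- Report the number of split doses separately.

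This brings 6.5.1 into line with 6.5. The cost is a few sentences of SAP text and one programming rule to join the two parts. The rule needs the infusion records to show which administrations fall on consecutive days, which should be confirmed against the eCRF because the documents do not show its structure. No dosing rule changes.

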6.5.2. Study Drug Compliance of Parsaclisib

For participants in the safety population, overall compliance (%) for parsaclisib will be calculated for all participants as follows:

$$\text{Compliance (\%)} = 100 \times (\text{total dose actually taken}) / (\text{total prescribed dose})$$

The total prescribed dose is defined as the sum of the doses prescribed by the investigator accounting for dose modifications.

The total actual dose taken for compliance will be calculated based on information entered on the Drug Accountability eCRF. If there are dispensed drugs that have not been returned yet, the actual dose taken starting from the dispense date of the unreturned drugs will be imputed by the dose taken as reported on the Dosing eCRF.

